AUC	Area under the concentration-time curve
ANOVA	Analysis of variance
BMI	Body mass index
CI	Confidence interval
CL	Clearance
C _{max}	Maximum activity
CV	Coefficient of variance
DSMC	Data Safety Monitoring Committee
eCRF	Electronic case report form
EMA	European Medicines Agency
FAS	Full analysis set
FVIII	Factor 8
HBV	Hepatitis B
HCV	Hepatitis C
HIV	Human immunodeficiency virus
kg	kilogram
IR	Incremental recovery
IU	International unit
IV	Intravenously
MedDRA	Medical Dictionary for Regulatory Activities Terminology
MRT	Mean residence time
PK	Pharmacokinetic
PKAS	Pharmacokinetic analysis set
PT	Prothrombin time
PTP	Previously treated patients
rFVIII	Recombinant factor 8
SD	Standard deviation

SAE	Serious adverse event
SAP	Statistical analysis plan
TEAE	Treatment-emergent adverse event
VWF	von Willebrand factor
V_{ss}	Volume of distribution at steady state

1. INTRODUCTION

This first-in-human study will evaluate the safety and tolerability of a single dose of BIVV001 administered intravenously (IV) in subjects with severe hemophilia A (defined as <1 IU/dL [$<1\%$] endogenous FVIII). In addition, this study will provide data on the pharmacokinetics (PK) of this drug compared with that of a commercially available recombinant FVIII (rFVIII) product (Advate).

This statistical analysis plan (SAP) describes the planned data summaries and statistical analyses to be performed for this study based on Protocol 242HA101 Version 6.0, dated 02 January 2018.

2. STUDY OBJECTIVES AND ENDPOINTS

2.1. Study Objectives

2.1.1. Primary Objective

The primary objective of the study is to assess the safety and tolerability of a single intravenous (IV) administration of BIVV001 in adult previously treated patients (PTPs) with severe hemophilia A.

2.1.2. Secondary Objective(s)

The secondary objective of the study is to characterize the PK of BIVV001 after a single IV administration compared with the PK of Advate, with FVIII activity measured by the one-stage (activated partial thromboplastin time [aPTT]-based) clotting assay.

2.1.3. Exploratory Objective(s)

The exploratory objective of the study is to characterize the PK of BIVV001 after a single IV administration compared with the PK of Advate, with FVIII activity measured by the two-stage chromogenic assay.

2.2. Study Endpoints

2.2.1. Primary Endpoint

The primary endpoints are as follows:

- The occurrence of adverse events (AEs)
- The occurrence of clinically significant abnormalities in laboratory tests, including development of inhibitors (neutralizing antibodies directed against FVIII) as determined by the Nijmegen-modified Bethesda assay

Details of the analysis of primary endpoints are described in [Section 9](#).

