9.2.1. Hematology and Chemistry

Hematology and chemistry data and change from baseline will be summarized over time using descriptive statistics for each drug and dose level group using the Safety Analysis Set. The data will also be presented in a listing using the Safety Analysis Set. A flag for lab results outside the reported normal range will be included in the listing. In addition, lab results that occur during a major surgical period will be flagged.

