9.2.2. Urinalysis

Urinalysis data will be presented in a listing using the Safety Analysis Set. A flag for lab results outside the reported normal range will be included in the listing. In addition, lab results that occur during a major surgical period will be flagged.

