9.2.3. Coagulation Parameters

Samples for coagulation parameters (PT, aPTT, D-dimer, international normalized ratio, thrombin-anti-thrombin, and prothrombin fragment 1.2, and vWF) will be collected at Screening, Visits 2 and 3 (pre-injection for Advate and 1, 6, and 24 hours post-injection), Visits 6 and 7 (pre-injection for BIVV001 and 1, 6, and 24 hours post-injection), Visit 14 (14 days post-injection for BIVV001), and at the End of Study/Early Termination Visit.

Hours from treatment will be calculated as the time elapsed from initiation of the Advate injection to sample collection for the Screening period and Advate treatment period or as the time elapsed from initiation of the BIVV001 injection to sample collection for the BIVV001 treatment period.

Coagulation data and change from baseline will be summarized over time using descriptive statistics for each drug and dose level group using the Safety Analysis Set. The data will also be presented in a data listing using the Safety Analysis Set.

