9.2.4. Inhibitor Development using the Nijmegen-modified Bethesda Assay

An inhibitor assessment using the Nijmegen-modified Bethesda assay will be performed for all subjects at Screening, Visit 2 (pre-injection for Advate), Visit 6 (pre-injection for BIVV001), Visit 14 (14 days post-injection for BIVV001) and the End of Study/Early Termination Visit.

The number and percentage of subjects who test positive for inhibitor will be presented for each drug by dose level. In addition, inhibitor status will be presented by dose level and subject in a listing using the Safety Analysis Set.

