9.2.5. Anti-rFVIIIFc-VWF-XTEN Antibodies

The plasma samples for anti-rFVIIIFc-VWF-XTEN antibody will be collected at Screening, Visit 2 (pre-injection for Advate), Visit 6 (pre-injection for BIVV001), Visit 14 (14 days post-injection for BIVV001) and the End of Study/Early Termination Visit.

The number and percentage of subjects who test positive for anti-rFVIIIFc-VWF-XTEN antibodies will be presented by dose level. In addition, antibody status will be presented by dose level and subject in a listing using the Safety Analysis Set.

[REDACTED]

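### The laboratory primary endpoint has no planned subject count for the routine panels, and events in a major surgical period are left out of the safety summary tables

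*SAP*

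**What the plan says.** **Laboratory endpoint.** Section 2.2.1 lists two primary endpoints: the occurrence of adverse events and "The occurrence of clinically significant abnormalities in laboratory tests, including development of inhibitors". It continues "Details of the analysis of primary endpoints are described in" Section 9. Section 9 then plans the following:

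- Section 9.2.1: "Hematology and chemistry data and change from baseline will be summarized over time using descriptive statistics for each drug and dose level group". For the listing, "A flag for lab results outside the reported normal range will be included in the listing".
- Section 9.2.2: "Urinalysis data will be presented in a listing using the Safety Analysis Set", with the same out-of-range flag.
- Section 9.2.3: "Coagulation data and change from baseline will be summarized over time using descriptive statistics for each drug and dose level group", plus a listing for which no flag is described.
- Section 9.2.4: "The number and percentage of subjects who test positive for inhibitor will be presented for each drug by dose level".
- Section 9.2.5: "The number and percentage of subjects who test positive for anti-rFVIIIFc-VWF-XTEN antibodies will be presented by dose level".

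Two general rules also apply. Section 5.1 leaves unscheduled-visit data out of analysis unless stated otherwise. Section 5.1.1.10 uses the last of several repeat assessments in a visit window.

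**Surgical period.** Section 5.1.1.7 runs the major surgical period from surgery to the resumption of routine prophylaxis or, if no resumption is recorded, to hospital discharge. Section 9.1 lists adverse events from that period separately and omits them from the AE summary tables. Section 9.2 restricts laboratory results from the surgery period to listings. Section 9.1.2 bases percentages on all Safety Analysis Set patients at the dose level.

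**The concern.** The occurrence of an abnormality is an event in a subject, and its natural summary is a number and percentage of subjects. The SAP uses that form for inhibitors and anti-drug antibodies but not for the other laboratory tests, although the endpoint wording makes inhibitors only one component. By-visit means, minima and maxima can reveal an extreme value, but they do not show how many subjects had one. An out-of-range flag does not identify a clinically significant result either.

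The surgical-period rule touches both primary endpoints. Leaving events out can lower a reported incidence and can never raise it. In a first-in-human safety study with about 18 subjects, each subject carries visible weight in the tables.

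**Working it through.** **1. Match each laboratory component to its planned output** (Sections 9.2 to 9.2.5 and the table list in Section 12.1).

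| Component | Planned summary | Flag in listing | Subject count |
|---|---|---|---|
| Hematology | values and change from baseline | out of range | none |
| Chemistry | values and change from baseline | out of range | none |
| Urinalysis | listing only | out of range | none |
| Coagulation and thrombosis markers | values and change from baseline | none described | none |
| Inhibitors | n (%) by drug and dose level | – | yes |
| Anti-drug antibodies | n (%) by dose level | – | yes |

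Of the 4 visible routine panels, 0 have a planned count of subjects with an abnormality. The visible laboratory tables in Section 12.1 are hematology, chemistry, coagulation, antibody status and inhibitor development, which agrees with the text.

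**2. Look for a rule elsewhere that supplies the count.** Sections 5.1 and 5.2.2 give counts and percentages for categorical data but name no laboratory-abnormality variable. Section 9.2 gives a positivity rule for inhibitors (at least 0.6 BU/mL, confirmed on a second sample) but no criterion of clinical significance for the other tests. Section 10 records two changes, to the interim analysis and to the PK analysis set, and neither concerns this endpoint.

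**3. Apply the default data rules.** An abnormal value from an unscheduled visit stays out of the summaries. An abnormal value repeated within the same window is replaced by the later one. These rules suit by-visit statistics, but for an endpoint of occurrence they can remove the very result that defines the event.

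**4. Size of the surgical-period exclusion.** Section 3.1 plans about 8 low-dose and about 10 high-dose subjects, and 8 + 10 = 18 agrees with its stated total. If a subject's only event in a row falls in the surgical period, the row loses 1/n:

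- n=8: 1/8 = 12.5 points
- n=10: 1/10 = 10.0 points
- n=18 (overall column): 1/18 = 5.6 points

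If the subject has another event in the same row outside the period, the row does not change. The SAP gives no frequency of major surgery, so no expected effect can be computed.

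**5. Is the denominator the cause?** Take n=8 with 2 affected subjects, one of them affected only during surgery. Counting all events gives 2/8 = 25.0%. The plan gives 1/8 = 12.5%. Removing that subject from the denominator as well gives 1/7 = 14.3%. The shortfall therefore comes almost entirely from the numerator.

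**6. Reach of the laboratory exclusion.** The inhibitor assay is among the tests listed in Section 9.2, and the surgery sentence at the end of that section has no exception. Read literally, a positive result sampled in that period could drop out of the count planned in Section 9.2.4.

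**The case against.** The strongest reply on the laboratory part is that the SAP is not the only document. The protocol may define clinical significance and may require such results to be recorded as adverse events. The tables in Sections 9.1.1 and 9.1.2 would then count them by subject. The table shells mentioned in Section 5.2.1 are not shown, and a title such as the chemistry summary does not rule out counts. Two test entries in Section 9.2, a block after Section 9.2.5 and one listing title are redacted. The one abnormality that the endpoint names, inhibitor development, is fully handled. All of this stands and limits confidence. It does not remove the gap: the SAP sends this endpoint to its own Section 9, and nothing visible there ties the routine panels to a table of occurrence or to the AE tables.

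On the surgical part, the rule is openly stated. The events are flagged in the full AE listing and have a dedicated listing, and all serious events and deaths are listed. Observation after the single BIVV001 dose lasts 28 days, so major surgery may never occur. That also stands. The rule nevertheless governs the incidence tables of a primary endpoint. Serious events are plausibly affected, because hospitalization is a seriousness criterion (Section 9.1.5) and the period can run to discharge.

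A reader might infer three stronger things, and the document supports none of them:

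- That safety data are concealed. They remain in listings.
- That the denominator is wrong. Using all treated subjects is ordinary for subject incidence, and step 5 shows that it matters little.
- That every surgical-period event lowers the reported incidence. Only a subject's sole event in a row does.

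**Conclusion.** The point holds on both parts and should be corrected, with moderate confidence. As written, the laboratory primary endpoint is tabulated as a subject count only for inhibitors and anti-drug antibodies. For 0 of the 4 visible routine panels is there a count of affected subjects, and the default rules keep some relevant results out of the summaries. This conclusion rests on the visible text and would weaken if the protocol records these results as adverse events or if the table shells contain the counts.

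The surgical-period rule can understate a row by one subject (12.5, 10.0 or 5.6 points at n=8, 10 or 18) for each subject whose only event in that row falls in the period. Any effect is downward, and it is zero if no subject has major surgery. I have taken the surgery period of Section 9.2 to mean the major surgical period of Section 5.1.1.7. No hypothesis test is affected, since none is planned.

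**What to change.** **Laboratory endpoint.** In Section 9.2, state the criterion for a clinically significant abnormality or cite where the protocol gives it. Add to Section 9.2 and Section 12.1 a table of n (%) of subjects with at least one post-dose clinically significant abnormality, by test, treatment period and dose level. Base it on all post-dose results, including unscheduled and repeat values, and keep the present rules for the by-visit statistics. Alternatively, if these results are recorded as adverse events, say so in Section 9.2 and name the AE table that reports the endpoint.

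**Surgical period.** Include treatment-emergent adverse events and serious adverse events from the major surgical period in the main AE tables, and add a supplementary summary that excludes them. State in Section 9.2 that inhibitor results are exempt from the surgery-period exclusion.

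**Cost.** SAP wording and one or two extra tables. Surgical-period adverse events are already flagged in the listing, so both versions can be produced directly. The SAP shows no recorded judgement of clinical significance. If none is collected, the criterion must be one that can be applied to the laboratory values. The downside is that some surgery-related events will appear in the main tables; the supplementary summary shows the result without them.

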2.2.2. Secondary Endpoint(s)

The secondary endpoints are PK parameters based on the one-stage ([aPTT]-based) clotting assay, including but not limited to the following:

- maximum activity (C_{max}), half-life, clearance (CL), volume of distribution at steady state (V_{ss}), area under the concentration-time curve from time 0 to infinity (AUC_{∞}), mean residence time (MRT), incremental recovery (IR), and time to 1% above baseline for FVIII activity

Details of the analysis of secondary endpoints are described in [Section 8](#).

2.2.3. Exploratory Endpoint(s)

The exploratory endpoints are PK parameters based on the two-stage chromogenic assay, including but not limited to the following:

- C_{max} , half-life, CL, V_{ss} , AUC_{∞} , MRT, IR, and time to 1% above baseline for FVIII activity

Details of the analysis of exploratory endpoints are described in [Section 8](#).

3. STUDY DESIGN

3.1. Overall Study Design

[figure not shown]
This is a Phase 1/2a, open-label, dose-escalation, multicenter study designed to evaluate the safety, tolerability, and PK of a single IV dose of BIVV001 in subjects with severe hemophilia A who have received at least 150 exposure days of prior FVIII treatment.

Approximately 18 male PTPs aged 18 to 65 years will be enrolled: approximately 8 subjects in the low-dose cohort (Advate 25 IU/kg and BIVV001 25 IU/kg) and approximately 10 subjects in a high-dose cohort (Advate 65 IU/kg and BIVV001 65 IU/kg).

Each subject will be dosed with Advate followed by a PK sampling period. Following a brief washout period, each subject will then be administered BIVV001 followed by a PK sampling period. Subjects will undergo safety observation for 28 days following the injection of BIVV001, including sample collection for inhibitor assessments 14 and 28 days after the injection of BIVV001. Subjects may resume treatment with their pre-study FVIII product during the 28-day observation period after completing Visit 14 activities (which include the 14-day inhibitor test). Only subjects with adequate samples for PK and inhibitor characterization following both Advate and BIVV001 dosing will be considered evaluable; additional subjects will be enrolled as needed to ensure that at least 6 subjects in the low-dose cohort and 8 subjects in the high-dose cohort provide evaluable PK and inhibitor data.

An independent Data Safety Monitoring Committee (DSMC) will evaluate the safety data from the study on an ongoing basis.

Figure 1: Study Schema

* Screening may be extended up to 120 days with prior Sponsor approval. If the Screening Period extends beyond 56 days, screening assessments must be repeated as specified in the protocol prior to dosing with Advate. Washout duration at least 96 hours (4 days) from the most recent FVIII dose (prestudy FVIII) for a conventional product, 120 hours (5 days) for an extended half-life FVIII product.

[figure not shown]
** Washout duration at least 72 hours (3 days) from the Advate dose for the BIVV001 low-dose cohort, and at least 96 hours (4 days) for the BIVV001 high-dose cohort.

3.2. Statistical Hypothesis

No formal statistical hypothesis will be tested.

3.3. Sample Size Considerations

The sample size for this study is based on the need to establish the initial safety profile of BIVV001 and characterize its PK profile. The number of subjects who have severe hemophilia A is small; thus, the determination of sample size for this study is constrained by subject availability. Approximately 18 subjects will be enrolled and treated. Additional subjects may be enrolled to ensure that at least 6 subjects from the low-dose cohort and 8 subjects from the high-dose cohort provide evaluable PK and inhibitor data.

3.4. Randomization and Blinding

This is an open-label study with no blinding or randomization.

3.5. Interim Analysis

No formal interim analyses are planned.

At least one interim analysis will be performed when at least 3 subjects in the low dose cohort have completed the 28-day safety observation period and have available safety and PK data.

This analysis will focus on baseline demographic information, adverse events, and pharmacokinetic data and will be of a descriptive nature. No formal hypothesis testing will be performed.

The DSMC will review safety summaries and listings on a quarterly interval as well as on an ad hoc basis, as needed. In addition, the DSMC will evaluate available data following the low dose cohort to determine the appropriateness of escalating to the high dose cohort once the following conditions have been met: a) inhibitor test results from samples collected 14 days after the BIVV001 injection are available for at least 6 of the 8 subjects in the low-dose cohort, and b) adequate PK sampling following the BIVV001 dose has been completed and safety assessment results through the end of PK sampling are available for all active subjects in the low-dose cohort. Further details are provided in the DSMC charter.

Other descriptive interim analyses may be performed as necessary to support dose regimen planning for future studies.

4. ANALYSIS POPULATIONS

4.1. All-Enrolled Analysis Set

The All-Enrolled Analysis Set is defined as all subjects who are enrolled into the study and have been assigned a unique subject identification number.

4.2. Safety Analysis Set

The Safety Analysis Set is defined as all subjects who receive at least one dose of Advate or BIVV001.

4.3. Pharmacokinetic Analysis Set (PKAS)

The Pharmacokinetic Analysis Set (PKAS) is defined as subjects who have adequate blood sample collections (following Advate or BIVV001 administration), to assess key PK parameters, as determined by the PK scientist.

5. DEFINITIONS AND DATA HANDLING

Statistical analysis is being performed by Bioverativ, using SAS® version 9.4 or higher and, where appropriate, additional validated software.

5.1. General Principles

In general, the following approaches will be used in the analysis and summary of safety and PK endpoints, unless otherwise specified in this SAP.

Safety and PK data will be summarized using standard summary statistics for continuous and categorical data. Data will be summarized by study drug and dose level.

Data collected at unscheduled visits will be excluded from analysis, unless otherwise specified. However, all analysis data, including data collected at unscheduled visits, will be listed in the subject data listings.

No statistical hypothesis testing is planned.

5.1.1. Definitions

5.1.1.1. Screening Period

The screening period starts after signing the study consent form and ends immediately prior to the first dose of Advate or BIVV001.

5.1.1.2. Advate Dosing and PK Profile Period

The Advate dosing and PK profile period is defined as the period starting at the dose of Advate and ending at the last Advate PK sampling time point.

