8.1. Summary of FVIII Activity

For Advate (FVIII) treatment, FVIII activity (one-stage clotting and chromogenic assays) will be assessed at screening, just prior to the administration of Advate (pre- dose of 25 IU/kg or 65 IU/kg) at 0.5, 1, 6, 24, 48, and 72 hours post-injection.

For BIVV001 treatment, FVIII activity (one-stage clotting and chromogenic assays) will be assessed just prior to the administration of BIVV001 and at 0.17, 0.5, 1, 3, 6, 9, 24, 48, 72, 96, 120, 168, and 240 hours (10 days) post injection for subjects administered the low dose of BIVV001 and additionally at 288 and 336 hours (14 days) post injection for those subjects administered the high dose of BIVV001 and at the End of Study/Early Termination Visit.

Hours from treatment will be calculated as the time elapsed from initiation of the Advate injection to sample collection for the Screening period and Advate treatment period or as the time elapsed from initiation of the BIVV001 injection to sample collection for the BIVV001 treatment period.

FVIII activity will be summarized by study drug, dose level, visit, and by one-stage clotting assay and two-stage chromogenic assay, respectively and presented in one data listing for each study drug for the Safety Analysis Set. Summary descriptive statistics will include the number of non-missing values, mean, geometric mean, standard deviation, percent coefficient of variation, minimum, and maximum.

FVIII activity versus time profiles will be plotted in both original and log scale for each subject by study drug for both assays. In addition, the mean FVIII activity versus time profiles at each dose level will be constructed for the two study drugs in the original and log scale for both assays.

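### At 65 IU/kg the SAP ends the Advate profile at 72 h and does not assign to it the FVIII sample already planned at 96 h or later, just before BIVV001

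*SAP*

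**What the plan says.** - **Advate schedule.** SAP Section 8.1 has one list for 25 and 65 IU/kg: a pre-dose sample, then samples "at 0.5, 1, 6, 24, 48, and 72 hours post-injection". Section 5.1.1.2 defines the Advate PK period as "starting at the dose of Advate and ending at the last Advate PK sampling time point", so it closes at 72 h.
- **BIVV001 schedule.** The same section lengthens BIVV001 sampling at the higher dose, from 240 h to 336 h. It also says that FVIII activity, by both assays, "will be assessed just prior to the administration of BIVV001".
- **Washout.** The schema footnote in Section 3.1 requires 72 h or more between Advate and BIVV001 at the low dose, and "at least 96 hours (4 days) for the BIVV001 high-dose cohort".
- **Use of the data.** Section 2.2.2 lists half-life and "time to 1% above baseline for FVIII activity" among the secondary endpoints. Section 8.2 compares both between drugs, separately by dose level, in a log-scale ANOVA with drug and subject as factors. It calculates individual parameters from actual times.
- **Method.** The opening of Section 8 leaves detailed PK methodology to the PK report.

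**The concern.** Moving from 25 to 65 IU/kg adds log2(65/25) = 1.38 half-lives before activity falls to the same level, yet the Advate profile stops at the same hour. If activity is still more than 1% above baseline at 72 h, time to 1% has to be projected from the late slope, which may rest on only the 24, 48 and 72 h samples.

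A later measurement of the same decline already exists for every high-dose subject who goes on to BIVV001, but the SAP gives it no role in Advate PK. It falls after the Advate PK period (Section 5.1.1.2) and before the BIVV001 PK period, which starts at the BIVV001 dose (Section 5.1.1.3). For safety, Section 5.1.1.4 counts that moment as Advate time.

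At stake is the precision of the comparator's half-life and time to 1% in a cohort of about 10 subjects, at least 8 of them evaluable. It is also left open whether a terminal sample enters the fit, in an open-label study where that choice could be made after the values are seen.

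**Working it through.** The SAP states no half-life, recovery or time-to-1% figure, so there is nothing of its own to reproduce.

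**Inputs from the SAP:** Advate dose D = 25 or 65 IU/kg; last Advate sample at 72 h; high-dose pre-BIVV001 sample at 96 h or later.

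**Assumptions, not in the SAP:** recovery R = 2 IU/dL per IU/kg (range 1.5 to 2.5); mono-exponential decline with half-life h; 1% taken as 1 IU/dL above baseline.

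**1. When does time to 1% lie beyond 72 h?** C(t) = D × R × 2^(−t/h), so T = h × log2(D × R), and T > 72 when h > 72 / log2(D × R).
- 65 IU/kg, R = 2: log2(130) = 7.02; 72/7.02 = 10.3 h.
- 65 IU/kg, R = 1.5: log2(97.5) = 6.61; 10.9 h.
- 65 IU/kg, R = 2.5: log2(162.5) = 7.34; 9.8 h.
- 25 IU/kg, R = 2, for contrast: log2(50) = 5.64; 12.8 h.

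With R = 2 and h = 12 h at 65 IU/kg, activity at 72 h is 130 × 2^(−6) = 2.03 IU/dL and T = 84 h.

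**2. What share of high-dose subjects is that?** Half-life was simulated as lognormal with CV 20 to 30%, and recovery with mean 2.0 to 2.5 and CV 20%. Share with T > 72 h, by geometric mean half-life:
- 9 h: 26–38%
- 10 h: 45–54%
- 11 h: 59–71%
- 12 h: 70–84%
- 13 h: 79–92%

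**3. What would the later sample show?** Activity at 96 h is at least 1 IU/dL when h ≥ 96/7.02 = 13.7 h (R = 2). At h = 12 h it is 130 × 2^(−8) = 0.51 IU/dL. At a geometric mean of 12 h and mean recovery 2.0, 70–78% of subjects cross after 72 h and 26–33% after 96 h. The 37–52% in between have a 96 h value below 1 IU/dL. If that value is quantifiable, their crossing can be interpolated. If not, it is only bracketed between 72 h and the sample.

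**4. Gain in the late slope where the sample is quantifiable.** With equal log-scale error, the slope SE is proportional to 1/√Sxx.
- Times 24, 48, 72: Sxx = 24² + 0 + 24² = 1152.
- Times 24, 48, 72, 96: Sxx = 36² + 12² + 12² + 36² = 2880.
- Ratio √(1152/2880) = 0.63, a 37% reduction.

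**5. Gain in the endpoint.** With log-scale error s = 0.15 (assumed), SD(T) ≈ s × √(1/n + (T − mean t)²/Sxx) / (ln 2/h).
- h = 16 h, T = 16 × 7.02 = 112 h: three points 0.15 × √(0.333 + 3.60)/0.0433 = 6.9 h; four points 0.15 × √(0.25 + 0.953)/0.0433 = 3.8 h. Simulation gave 7.2 and 3.9 h, and for half-life 1.7 and 1.05 h.
- h = 14 h, T = 98 h: simulation gave 4.9 and 2.7 h.
- h = 12 h, T = 84 h, three points: 0.15 × √(0.333 + 1.144)/0.0578 = 3.2 h, just under 4% of T.

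**6. AUC.** The fraction beyond 72 h is 2^(−72/h): 1.6% at h = 12 h and 4.4% at h = 16 h. Little changes there.

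**The case against.** A reader might infer three stronger points that the SAP does not support.

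- **That Advate's time to 1% usually has to be extrapolated at 65 IU/kg.** This needs a half-life and recovery that the SAP does not state. Over plausible values the share runs from about a quarter to about nine tenths.
- **That the pre-BIVV001 sample is discarded.** No sentence excludes it. Section 8.1 lists it under BIVV001, but also counts hours from Advate for samples in the Advate treatment period, and Section 9.1 runs that period for adverse events until BIVV001 is given. Section 8.2 excludes no sample, Section 4.3 leaves adequacy to the PK scientist, and Section 8 defers methodology. The accurate statement is that the SAP does not assign the sample to the Advate profile.
- **That the precision gain at a 16 h half-life is typical.** It is a favourable case. The washout is a minimum, so the sample may also fall later than 96 h, at lower activity. The SAP gives no quantification limit.

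The consequence is also modest. Even at 16 h, an SD of 7.2 h on 112 h is 6.4% per subject, or 6.4/√9 = 2.1% on a mean of nine. No hypothesis is tested. The schedule itself is a design matter for the protocol, which is not at hand, and is not challenged here.

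These limits stand. The deferral to the PK report does not remove the point, because the SAP itself sets out the schedule and the boundaries of each profile, and leaves this sample outside both PK periods.

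**Conclusion.** The point holds as a free improvement of limited size. At 65 IU/kg the Advate profile closes at 72 h, and a planned FVIII result at 96 h or later has no stated role in it. Time to 1% then lies beyond the profile for half-lives above about 9.8 to 10.9 h, given recovery of 2.5 down to 1.5 IU/dL per IU/kg and mono-exponential decline. Whether that is a minority, half or most of the cohort turns on Advate's typical half-life.

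The slope gain of up to about 37% applies where the sample is quantifiable, is taken at 96 h and joins a three-point late fit. If 1 IU/dL were the limit, that means half-lives above about 13.7 h at recovery 2. Below the limit the sample only shows that 1% had already been crossed. The 96 h timing is guaranteed in the high-dose cohort only.

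**What to change.** In Sections 5.1.1.2 and 8.1/8.2, for the high-dose cohort:

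1. State that a quantifiable pre-BIVV001 FVIII result, at its actual elapsed time from the Advate injection, is also the last point of the Advate profile for half-life, AUC and time to 1%, by both assays, provided no other FVIII was given since Advate.
2. State that a below-limit result serves only as a descriptive check on the extrapolated time to 1%. It should not enter the ANOVA in Section 8.2, because that model has no means of handling a bound in place of a value.
3. Report, by drug and dose level, how many time-to-1% values are extrapolated beyond the last sample.

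The cost is SAP wording and one added count in the PK tables. The sample and both assays are already planned, and Section 8.2 already works with actual times, so the varying time of this sample needs no new rule.
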